2. Admission to the **Intensive Care Unit (ICU) for more than 48 hours**.
3. Availability of **chest CT imaging data**.

Exclusion Criteria

1. Patients aged <18 years.
2. Patients with incomplete medical records.
3. Absence of chest CT imaging or presence of technically inadequate/uninterpretable chest CT images.

Sample Size and Data Partitioning

This study is designed as a multicenter, large-sample, retrospective observational study and plans to include a total of 400 patients with ARDS who meet the eligibility criteria. Of these, 300 cases will be contributed by the primary institution and Sub-center 1, and 100 cases by Sub-center 2.

The study does not involve conventional experimental or control groups. Instead, cases will be partitioned into three datasets according to the model development workflow:

Training set: 276 cases (approximately 80% of the combined cases from the primary institution and Sub-center 2), obtained through stratified random sampling to preserve the distribution of mild, moderate, and severe ARDS;

Internal validation set: 69 cases (approximately 20% of cases from the same two centers), used to monitor overfitting and optimize model hyperparameters;

External test set: 55 cases, all derived from Sub-center 1 and entirely independent of the model development process, used to evaluate model generalizability.

Primary Outcome Measures

The primary outcomes of this study focus on the overall effectiveness of the proposed AI-based framework across three key clinical tasks:

(1) Accuracy of ARDS severity classification, defined as the agreement between model-predicted ARDS severity (mild, moderate, or severe) and the reference clinical classification based on the 2023 global ARDS criteria, assessed using chest CT images obtained within 24 hours of ICU admission;

(2) Treatment plan matching rate, defined as concordance between model-recommended and actual clinical management across five intervention modalities (mechanical ventilation, high-flow oxygen therapy, non-invasive ventilation, prone positioning, and neuromuscular blockade), evaluated at the time of index chest CT acquisition;

(3) Accuracy of 28-day in-hospital mortality prediction, defined as the ability of the model to predict all-cause in-hospital mortality within 28 days of ICU admission.

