These three outcomes collectively reflect the overall effectiveness of the model within a closed-loop framework encompassing disease stratification, treatment recommendation, and prognosis prediction.

Secondary Outcome Measures

Secondary outcomes include comparative performance improvement of the proposed model over commonly used baseline AI models; calibration performance of mortality prediction; interpretability analyses based on imaging-derived and clinical feature contributions; and assessment of the association between treatment concordance and 28-day in-hospital mortality using multivariable regression models.

Research procedures

1. Data collection

(1) Demographic and Baseline Clinical Data

Age, sex, body mass index (BMI), comorbidities (including chronic kidney disease, coronary artery disease, hypertension, diabetes, liver cirrhosis, HIV infection, etc.), primary etiology of ARDS, and receipt of mechanical ventilation, high-flow nasal oxygen therapy, or ECMO. BMI is calculated as weight (kg) divided by height squared (m^2).

(2) Physiologic Parameters

Body temperature (T), heart rate (HR), respiratory rate (RR), peripheral oxygen saturation (SpO_2), and mean arterial pressure (MAP).

(3) Laboratory Parameters

pH, partial pressure of arterial oxygen (PaO_2), fraction of inspired oxygen (FiO_2), partial pressure of arterial carbon dioxide (PCO_2), lactate (Lac), platelet count (PLT), white blood cell count (WBC), hemoglobin (Hb), serum creatinine, C-reactive protein (CRP), procalcitonin (PCT), international normalized ratio (INR), B-type natriuretic peptide (BNP), and interleukin-6 (IL-6).

(4) Ventilator or High-Flow Oxygen Parameters

Positive end-expiratory pressure (PEEP), tidal volume (TV), plateau pressure (Pplat), and flow rate (FLOW).

(5) Other Clinical Scores

Sequential Organ Failure Assessment (SOFA) score and Acute Physiology and Chronic Health Evaluation II (APACHE II) score.

2. CT Equipment and Scanning Parameters

Chest CT images included in this study were acquired from two CT scanners with the following parameters:

CT1 (64-slice): Manufacturer: Philips; Model: Brilliance; Tube voltage: 120 kV; Tube current: 1000 mA; Slice thickness: 5 mm; Slice interval: 5 mm; Pitch: 0.789:1.

CT2 (128-slice): Manufacturer: United Imaging; Model: uCTR760; Tube voltage: 120 kV; Tube current: 1000 mA; Slice thickness: 5 mm; Slice interval: 5 mm; Pitch: 0.984:1.

3. Quantitative Assessment of ARDS

Preliminary Image Processing

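### Exclusion for incomplete records is undefined and is the plan's only rule for missing clinical data; depending on how it is applied, it can select the cohort by treatment and possibly by outcome

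*Combined protocol and SAP*

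**What the plan says.** Under Exclusion Criteria, item 2 reads "Patients with incomplete medical records". No field, time window or threshold is attached. Item 3 deals separately with absent or unreadable CT.

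Research procedures, section 1 (Data collection), lists what is gathered. Besides demographics, comorbidities, etiology and support received, there are five vital signs, fourteen laboratory values (among them procalcitonin, BNP and IL-6), four device settings, and "Sequential Organ Failure Assessment (SOFA) score and Acute Physiology and Chronic Health Evaluation II (APACHE II) score". The device settings come under the heading "Ventilator or High-Flow Oxygen Parameters". Nothing in the section says that a record lacking one of these items is incomplete.

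The section on etiological and respiratory mechanics classification feeds structured clinical variables and respiratory mechanics into the multimodal model. Under Primary Outcome Measures, outcome 2 scores agreement on "mechanical ventilation, high-flow oxygen therapy, non-invasive ventilation, prone positioning, and neuromuscular blockade", and outcome 3 is death in hospital within 28 days of ICU admission. The Statistical Analysis Plan contains no imputation, no coding of missing values, no comparison of excluded with included patients, and no complete-case sensitivity analysis.

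**The concern.** A retrospective cohort drawn from routine records will have gaps, and the only tool the plan offers for gaps in clinical data is to leave the patient out. Two kinds of listed value make this hazardous. Some tests, such as IL-6, BNP and procalcitonin, are usually ordered selectively (general clinical knowledge; the documents do not say). Some settings depend on the device: a patient on high-flow oxygen has no plateau pressure. Requiring such values would remove patients because of the support they received, which is what outcome 2 asks the model to predict.

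Completeness may also track outcome, which would shift the mortality mix on which outcome 3 and the calibration analysis depend. Because the term is undefined, the three hospitals may apply it differently, so that development and external test patients differ for reasons unrelated to disease. That works against the secondary objective of showing applicability in real-world settings. A tool developed only on complete records would also meet gaps in use that it never saw in training.

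**Working it through.** **1. The plan's own figure.** From Sample size estimation: 15 predictors × 10 events = 150 deaths; 150 / 0.375 = 400. This reproduces. Sample Size and Data Partitioning counts the 400 among patients who meet the eligibility criteria, so criterion 2 acts before the count and does not itself reduce N.

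**2. Count of listed values.** 5 physiologic + 14 laboratory + 4 device + 2 scores = 25, or 21 without the device group.

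**3. Complete-record share if every value were required.** Assume each of k values is missing independently in a proportion q of patients. The share complete is (1 − q)^k. No q is given in the documents.

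| q (assumed) | k = 25 | k = 21 | k = 14 (laboratory only) |
|---|---|---|---|
| 1% | 78% | 81% | 87% |
| 2% | 60% | 65% | 75% |
| 5% | 28% | 34% | 49% |
| 10% | 7% | 11% | 23% |

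These figures are illustrative only and probably overstate the loss. Blood-gas items tend to be measured together, as do blood-count items, and the two scores overlap other listed values. Positive correlation raises the complete share. The k = 25 column also treats device settings as randomly missing, when for some patients they do not exist at all.

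**4. Loss by treatment.** If plateau pressure and tidal volume were required of everyone, and 10%, 20%, 30% or 50% of patients were never invasively ventilated (assumed), then 40, 80, 120 or 200 of every 400 candidates would be removed for that reason alone (400 × share).

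**5. Effect on mortality.** Let p = 0.375, and let c_s and c_d be the assumed proportions of survivors and deaths with complete records. Retained mortality = p·c_d / (p·c_d + (1 − p)·c_s). The 37.5% is the plan's historical in-ICU rate, used here in place of 28-day in-hospital mortality.

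| c_s | c_d | Retained mortality | Deaths in 400 | Deaths per predictor (15) |
|---|---|---|---|---|
| 80% | 80% | 37.5% | 150 | 10.0 |
| 80% | 70% | 34.4% | 138 | 9.2 |
| 80% | 60% | 31.0% | 124 | 8.3 |
| 80% | 40% | 23.1% | 92 | 6.2 |
| 60% | 80% | 44.4% | 178 | 11.9 |

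Example, third row: 0.375 × 0.6 = 0.225; 0.625 × 0.8 = 0.500; 0.225 / 0.725 = 0.310. Equal completeness leaves mortality unchanged. Unequal completeness moves it either way, and the plan has nothing that would detect this.

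**The case against.** A reader might infer that the criterion requires all 25 values and therefore does select the cohort by treatment and outcome. The documents do not support that. No sentence ties incompleteness to the data-collection list. The word joining the two devices in "Ventilator or High-Flow Oxygen Parameters" suggests that settings are expected only where the device is in use. Since high-flow oxygen and non-invasive ventilation are scored in outcome 2, patients on them are plainly meant to be in the cohort.

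Selection by outcome is plausible but undocumented. The requirement of more than 48 hours in ICU already removes the earliest deaths and departures, and the remaining mechanisms can oppose each other: patients who die may have fewer values, but so may less closely monitored survivors. The percentages in step 3 rest on assumed rates and an unrealistic independence assumption.

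All of this stands, and it makes the point conditional. It does not remove it. If the lenient reading is intended, missing and not-applicable values stay in the data, and the plan does not say how the multimodal model, the mortality regression or any LASSO using clinical values will treat them. The strict reading can select the cohort; the lenient one leaves the analysis unspecified.

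**Conclusion.** The point holds in conditional form. Criterion 2 is undefined, it is the only rule for missing clinical data, and if applied to the listed values it can select patients by treatment and possibly by outcome, and can do so differently by centre. Neither size nor direction can be derived from the documents. The 23.1% to 44.4% range for retained mortality depends wholly on assumed completeness rates and shows only that the effect could matter for calibration and for the 10-events-per-predictor target. The (1 − q)^k shares should not be read as expected losses, nor the point as a shortfall in the 400. The plan should be changed here, because a better rule is available at little cost.

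**What to change.** Restrict criterion 2 to patients who lack any of the following:

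- the index CT (absent or unreadable scans are already covered by criterion 3);
- the data needed for the reference severity class;
- the record of the five treatment modalities at index CT, without which outcome 2 cannot be scored;
- in-hospital status to day 28, with discharge alive before day 28 counted as known, since the outcome is in-hospital death.

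Keep everyone else. Code device-specific settings as not applicable where the device was not in use. Impute other missing predictors with a model fitted on training data only and applied unchanged to the validation and test sets; use multiple imputation in any logistic or LASSO model that uses clinical values.

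One safeguard is needed. Device settings, their not-applicable codes and their missingness indicators reveal the type of support, so they must be kept out of the inputs to the treatment-recommendation head; otherwise they give away the label of outcome 2.

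Show complete-case results as a sensitivity analysis, and report exclusions by reason, centre, treatment and outcome.

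The cost is one reworded criterion, a short missing-data paragraph and some extra analysis. The downside is reliance on an imputation assumption; comparison with the complete-case results will show how sensitive the findings are to that choice.

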The sample size was preliminarily estimated using the event-per-variable principle. The mortality prediction component is designed to include no more than 15 candidate predictors in the final multivariable logistic regression model. Following the commonly accepted criterion of at least 10 outcome events per predictor, a minimum of 150 death

events is required to ensure model stability and interpretability. Based on historical data from the participating centers, the in-ICU mortality rate among patients with ARDS is approximately 37.5%. Accordingly, the total target sample size for this study is estimated to be approximately 400 patients.

Statistical Analysis Plan

All eligible cases will be stratified and randomly sampled at an 8:2 ratio within Shanghai General Hospital and its affiliated centers to form the model training set and internal validation set. Cases from an additional participating center will be reserved as an independent external test cohort.

Model performance will be evaluated for three predefined tasks: ARDS severity classification, treatment strategy prediction, and mortality risk prediction. Performance metrics will include accuracy, balanced accuracy, area under the receiver operating characteristic curve (AUC), precision–recall curve analysis, and the Brier score. During model development, five independent repeated experiments will be conducted, and performance will be reported as mean values with standard deviations.

For comparative performance assessment, results from the five independent experiments will be compared using two-sided Wilcoxon rank-sum tests, with a significance threshold of 0.05. Different levels of statistical significance will be denoted using conventional symbols (e.g., “*”, “**”) corresponding to predefined P-value ranges.

To assess the association between model outputs and clinical outcomes, model-recommended intervention sets will first be encoded for agreement with actual clinical management. These agreement variables will then be incorporated into multivariable logistic regression models together with six imaging-derived anatomical features (e.g., diaphragmatic height, lung volume). Adjusted odds ratios with 95% confidence intervals will be reported, and a two-sided P value <0.05 will be considered statistically significant.

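### The training/validation split names only ARDS severity as a stratification factor; adding 28-day death would remove avoidable noise from internal mortality calibration at almost no cost

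*Combined protocol and SAP*

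**What the plan says.** Sample Size and Data Partitioning places 276 patients in training, "obtained through stratified random sampling to preserve the distribution of mild, moderate, and severe ARDS". No other factor is named there. The same section gives the role of the second set: "Internal validation set: 69 cases (approximately 20% of cases from the same two centers), used to monitor overfitting and optimize model hyperparameters". The third set stands apart: "External test set: 55 cases, all derived from Sub-center 1 and entirely independent of the model development process".

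Two other sections describe the split, and both call it stratified without naming a variable. The Statistical Analysis Plan has cases "stratified and randomly sampled at an 8:2 ratio within Shanghai General Hospital and its affiliated centers", with a further centre held back for external testing. Preliminary Image Processing divides the data 60/20/20 and uses the validation part to choose the best model.

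Death within 28 days in hospital is the third primary outcome, and calibration of the mortality prediction is a secondary outcome. Sample size estimation is built on deaths: it allows "no more than 15 candidate predictors" and states that "the in-ICU mortality rate among patients with ARDS is approximately 37.5"%.

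**The concern.** One split serves three tasks, but only the label of the severity task is held in balance. The study is retrospective, so vital status can be known for every patient before the split is drawn. Leaving it to chance is therefore avoidable.

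If the validation set happens to hold too many or too few deaths, measures that depend on the death rate move for reasons unrelated to the model. Observed-minus-predicted mortality shifts most. The Brier score and the precision-recall curve shift too, and a difference between training and validation performance becomes harder to read as overfitting.

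**Working it through.** **The plan's own figures.** Events per variable: 15 predictors × 10 events = 150 deaths, and 150 / 0.375 = 400 patients, as stated. Split: 276 + 69 = 345, with 276/345 = 80.0% and 69/345 = 20.0%. Adding the 55 external patients gives 400. Centres: "300 cases will be contributed by the primary institution and Sub-center 1, and 100 cases by Sub-center 2", so the primary institution supplies 345 − 100 = 245 of the development pool. All of these reproduce.

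**Assumption on mortality.** The documents give in-ICU mortality (37.5%), not 28-day in-hospital mortality. I use 37.5% as a proxy and show 25% to 45%.

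**Death left to chance, no stratification.** The pool has 345 × 0.375 ≈ 129 deaths. The number of deaths x in the 69 is hypergeometric(345, 129, 69).

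- Mean = 129 × 69/345 = 25.8
- SD = √[69 × (129/345) × (216/345) × (276/344)] = 3.6
- 95% range = 19 to 33 deaths, that is 28% to 48%

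The mortality gap, validation minus training, is x/69 − (129 − x)/276 = (5x − 129)/276. Its SD is 5 × 3.6/276 = 6.5 points. A gap of 10 points or more needs x ≤ 20 (−10.5 points) or x ≥ 32 (+11.2 points).

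| Assumed mortality | Deaths in 345 | SD of gap (points) | P(gap ≥ 10 points) |
|---|---|---|---|
| 25% | 86 | 5.8 | 8.7% |
| 30% | 104 | 6.2 | 10.7% |
| 37.5% | 129 | 6.5 | 12.6% |
| 45% | 155 | 6.7 | 13.6% |

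At 37.5%, a gap of 15 points or more has probability 1.8%.

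**After severity stratification.** The documents give neither severity shares nor mortality by severity, so both are assumed here (400,000 simulated splits each).

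| Shares, mild/moderate/severe | Mortality, mild/moderate/severe | P(gap ≥ 10 points) |
|---|---|---|
| 30/45/25% | 28/37/50% | 12.2% |
| 30/45/25% | 20/37/60% | 10.8% |
| 33/34/33% | 10/35/67.5% (extreme) | 8.0% |

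Balancing severity therefore does little to balance death.

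**What death stratification changes.** With death as a factor, the 69 hold 25 or 26 deaths: (125 − 129)/276 = −1.4 points or (130 − 129)/276 = +0.4 points. Allowing 24 to 28 deaths for rounding across severity-by-death cells, the gap runs from −3.3 to +4.0 points. A 10-point gap cannot occur.

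**Effect on the metrics.** This was simulated with assumed mortality models: 69 validation patients, 37.5% mortality, and two correlated, calibrated models with AUC about 0.76 and 0.70.

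| Quantity in the validation set | Random split | Death-stratified |
|---|---|---|
| SD of observed minus predicted mortality | 4.8 points | 2.4 points |
| SD of one model's Brier score | 0.0226 | 0.0208 |
| SD of the paired Brier difference between models | about 0.016 to 0.017 | unchanged |
| Better model chosen | about 87% to 89% | about 86% to 89% |

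The calibration error halves. The single-model Brier SD falls by (0.0226 − 0.0208)/0.0226 = 8%. Model choice does not improve.

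**The case against.** The strongest reply is that a random split is unbiased and that candidate models are compared on the same 69 patients. A shift in the death rate moves their Brier scores together and largely cancels in the ranking. The simulation bears this out, so a reader who infers that the imbalance corrupts model selection goes too far. The noise in selection comes from having 69 patients, which stratification leaves unchanged. This part of the reply stands.

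Three further inferences are tempting and are not supported:

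- **Thresholds.** One might suppose that mortality cut-offs are set on the validation set. The plan mentions only overfitting and hyperparameters there; no decision threshold for mortality is described.
- **Centre.** One might say that centre is also left to chance. The Statistical Analysis Plan's word *within* can mean sampling inside each centre, and its stratification variable is unnamed. Only if the draw is pooled would the number of Sub-center 2 patients in the 69 vary from 14 to 27 (expected 20), with about a 10% chance of a 10-point gap in centre share.
- **External performance.** The 55 external patients are not part of this split, so the generalizability estimate is unaffected.

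It can also be said that severity is a legitimate stratifier for a study whose primary objective is a severity model, and that five repeated experiments are planned. The first is true but does not argue against adding a second factor. The second helps only if each repeat redraws the split, which is not stated. What the reply does not answer is the halving of calibration error at negligible cost.

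**Conclusion.** The point holds as a minor, nearly free improvement. Severity is the only stratification factor named, and nothing in the documents balances 28-day death. The typical mortality gap between the two sets is about 6.5 points. A gap of 10 points or more is a tail event: about 13% of splits at 37.5% mortality, 9% to 14% over mortality of 25% to 45%, and about 8% to 12% once severity is stratified.

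The consequence is extra noise in internal-validation mortality calibration, with a small effect on the Brier score and on the training-versus-validation overfitting check. It is not bias, and it is not a material threat to model ranking. The figures rest on in-ICU mortality standing in for the 28-day outcome, on assumed severity shares and gradients, and on assumed mortality models.

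**What to change.** Stratify the 8:2 split by severity class and 28-day in-hospital death (3 × 2 = 6 cells). If a cell is very small, merge severity classes within death. State whether sampling is already done per centre; if it is not, add centre (12 cells). With rounding to the nearest patient in six death cells, the validation deaths would then lie within 25.8 ± 3, that is 23 to 28. The gap would run from (115 − 129)/276 = −5.1 to (140 − 129)/276 = +4.0 points, still well short of 10.

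Name the stratification variables once, record the seed, say whether the five repeats redraw the split, and report deaths by set and centre. Do this when the three descriptions of the partition (276/69/55, 60/20/20, and 8:2 plus an external centre) are reconciled, since the refinement needs one agreed split to apply to. The cost is one line in the partition code and a sentence or two in the protocol; no extra patients or data are needed.

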Chest CT images for all enrolled cases were exported from the hospital Picture Archiving and Communication System (PACS) in DICOM format. To minimize inter-scanner variability, all non-contrast CT images underwent standardized preprocessing. Using Python (version 3.9.13) and the open-source SimpleITK library (version 2.2.1), all images were converted to NIFTI format. Subsequently, each image was normalized to arrays with a uniform mean and standard deviation to reduce distributional differences across scanners. Following preprocessing, the images were fed into the deep learning (DL) model.

For dataset partitioning, the “createDataPartition” function from the *caret* package was used to perform stratified random sampling, assigning 60% of the data to the training set, 20% to the validation set, and the remaining 20% to the test set. The training set was used to fit the machine learning model, the validation set to select the best-performing model, and the test set to evaluate the final model performance.

Construction of a Deep-Learning Lung Segmentation Model

This study focuses on chest CT images with the lung as the organ of interest; therefore, the lung will be defined as the region of interest (ROI) for the deep-learning (DL) model. We plan to develop a U-shaped Transformer-based model for lung segmentation, with target classes including lesion regions, the whole lung, individual lobes, and all bronchopulmonary segments.

The U-Net architecture is widely used for medical image segmentation and comprises an encoder, a decoder, and skip connections. The encoder extracts local image features through successive convolutional operations and employs down-sampling to progressively expand the network receptive field. Conversely, the decoder upsamples processed features back to the original image resolution to enable pixel-level semantic inference. Skip connections fuse features from corresponding encoder and decoder layers, ensuring comprehensive feature maps that preserve precise spatial information alongside high-level semantics, which is critical for accurate segmentation. A Transformer can serve as the backbone within the U-Net encoder/decoder blocks; by using global attention mechanisms, it captures long-range dependencies and, in principle, attains a global receptive field.

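### The plan does not say which patients score the five development runs; if it is the 69 tuning cases, internal performance is optimistic, and nested five-fold cross-validation of the 345 would avoid this

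*Combined protocol and SAP*

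**What the plan says.** Three sections of the combined protocol and SAP bear on this.

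- **Sample Size and Data Partitioning** sets 276 training, 69 internal validation and 55 external cases. The only role it gives the 69 is: "used to monitor overfitting and optimize model hyperparameters". The external cases are protected: "External test set: 55 cases, all derived from Sub-center 1 and entirely independent of the model development process, used to evaluate model generalizability".
- **Statistical Analysis Plan** divides the development cases 8:2 "to form the model training set and internal validation set", and reserves another centre for external testing. It continues: "During model development, five independent repeated experiments will be conducted, and performance will be reported as mean values with standard deviations". For model comparison, "results from the five independent experiments will be compared using two-sided Wilcoxon rank-sum tests, with a significance threshold of 0.05". It does not name the patients on which these runs are scored, or say whether the runs differ by random seed or by split.
- **Preliminary Image Processing** (under Quantitative Assessment of ARDS) describes a different partition, "assigning 60% of the data to the training set, 20% to the validation set, and the remaining 20% to the test set". There the validation set picks the model and the test set gives its final performance.

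Improvement over baseline AI models is a secondary outcome. Generalisability across centres is part of the secondary objective. No cross-validation or nested tuning is described anywhere.

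**The concern.** A set used to choose hyperparameters cannot also give an unbiased estimate of the chosen model's performance. The winning configuration is partly the one that chance favoured on those patients. Under 276/69/55 the only internal cases outside training are the 69 tuning cases, so internal figures reported under that plan have no clean source.

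Two readings of the results are at stake. All three primary outcomes are measures of model performance, so an inflated internal figure overstates the headline result. Generalisability will also be judged from the gap between internal and external performance. If the internal figure is too high, tuning bias can be mistaken for a centre or scanner effect. The comparison with baselines may be affected too, but only if the proposed model is tuned over more configurations than they are.

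**Working it through.** **1. The plan's own sizes reproduce.** Sample size estimation: 15 predictors × 10 events = 150 deaths, and 150 / 0.375 = 400. Partition: 400 − 55 = 345; 0.80 × 345 = 276; 0.20 × 345 = 69; 276 + 69 + 55 = 400.

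**2. The two partitions are incompatible.** A 60/20/20 split of 400 gives 240/80/80. Applied to the 345 development cases it gives 207/69/69. Neither has 276 training cases.

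**3. Which patients could score the five runs?**
- The 55 external cases: scoring them in development-phase runs would sit badly with their independence from development.
- The 20% test set of Preliminary Image Processing: it does not exist under 276/69/55 or under the SAP's 8:2 split.
- The 276 training cases or the 69 tuning cases: these are what remain, and both give optimistic figures.

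The 69 tuning cases are therefore the natural reading, but this is an inference. The same problem arises if the runs are five fresh 8:2 splits, each tuned and scored on the same 69.

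**4. Size of the optimism, if the 69 are used.** Expected deaths are 0.375 × 69 = 25.9, taken as 26, leaving 43 survivors. (The 37.5% is an in-ICU rate, used here for 28-day in-hospital death.) The simulation uses binormal scores. Every one of K configurations has a true AUC of 0.75, and the best of K on the same 69 patients is reported. Optimism is the mean best AUC minus 0.75. K, the true AUC and the correlation between configurations' scores are assumptions; the documents give none of them.

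| Configurations K | Score correlation | Optimism (AUC) |
|---|---|---|
| 10 | 0.8 to 0.5 | 0.04 to 0.07 |
| 20 | 0.8 to 0.5 | 0.05 to 0.08 |
| 50 | 0.8 to 0.5 | 0.06 to 0.09 |
| 5 to 50 | 0.9 | 0.02 to 0.05 |
| 20 | 0.95 | 0.03 |

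Across K = 5 to 50 and correlations from 0.95 down to 0.5, the range is about 0.02 to 0.09. If true AUCs also vary between configurations (SD 0.03), K = 20 gives about 0.02 at correlation 0.9 and 0.01 at 0.95.

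A parallel simulation for accuracy, with K = 5 to 50 and correlation from 0.9 down to 0, gives 3.1 to 10.1 points at a true accuracy of 0.80 and 3.3 to 11.9 points at 0.70.

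**5. Precision.** The Hanley-McNeil variance is [A(1−A) + (n₁−1)(Q₁−A²) + (n₂−1)(Q₂−A²)] / (n₁n₂), with Q₁ = A/(2−A) and Q₂ = 2A²/(1+A). At A = 0.75: Q₁ = 0.6, Q₂ = 0.6429, A² = 0.5625.
- 69 cases (26/43): (0.1875 + 25 × 0.0375 + 42 × 0.0804) / 1118 = 0.00402, so SE = 0.063.
- 345 cases (129/216): (0.1875 + 128 × 0.0375 + 215 × 0.0804) / 27864 = 0.00080, so SE = 0.028.
- External 55 (0.375 × 55 = 20.6, so 21/34): SE is about 0.07.

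The figure for 345 treats pooled out-of-fold predictions as independent, so it is approximate.

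**6. Fit of five folds, and of the test.** 345 / 5 = 69 held out and 345 − 69 = 276 trained on, so the stated sizes are unchanged. Nesting is essential: if configurations are chosen on the held-out folds themselves, simulated accuracy optimism is still about 1.3 to 5.5 points.

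The smallest two-sided p-value for a rank-sum test of five against five is 2/C(10,5) = 2/252 = 0.0079. But folds are paired and share training data, so an independent-samples test does not suit them. A signed-rank test on five pairs has a minimum of 2/2⁵ = 0.0625 and can never reach 0.05.

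**The case against.** A reader might infer that the plan commits to reporting performance on the tuning cases. It does not. The 69 are given a tuning role only, and the SAP leaves the scoring set unnamed. Preliminary Image Processing separates model selection from final evaluation, which is the right principle. The plan also keeps 55 external cases out of development, and judging a tuned model on an untouched set is conventional practice. These points stand: the text shows an ambiguity with a likely bias behind it, not a demonstrated bias. They do not settle the matter, because the separate internal test set belongs to a partition that the other two sections contradict, and the SAP still reports and tests results from the development phase.

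A reader might also infer that the comparison with baselines must favour the proposed model. The documents do not support this, because they say nothing about tuning budgets. With equal tuning, absolute figures are inflated but the direction of any bias in the difference is unclear. Equally, nothing in the SAP requires equal tuning.

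Finally, the simulated optimism depends on assumed inputs, and making all configurations equally good leaves nothing real to gain from selection. That is why the range extends down to 0.02 and is lower still if configurations truly differ.

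**Conclusion.** The concern holds conditionally. Internal results are optimistic if the five runs are scored on the 69 tuning cases, which is the natural reading of the partitioning section and the SAP together. Under the assumptions of step 4 the size is about 0.02 to 0.09 AUC. For comparison, the AUC standard error on 69 patients is 0.063. The external estimate is unaffected while Sub-center 1 stays untouched, although it is imprecise. This should be fixed, and before tuning starts, because tuning on the 69 cannot be undone afterwards. Nested five-fold cross-validation is worth adopting beyond the clarification, since it fits the stated sizes exactly and needs no new patients.

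**What to change.** 1. Reconcile Sample Size and Data Partitioning, Preliminary Image Processing and the Statistical Analysis Plan to one partition, and name the patients on whom each reported figure is computed.
2. Make the five runs a stratified five-fold cross-validation of the 345 development cases (276/69 per fold). Tune only on an inner split of each 276, and score each held-out 69 once.
3. Report pooled out-of-fold performance on all 345 as the internal validation.
4. Tune every baseline on the same folds with the same budget.
5. Replace the five-value Wilcoxon rank-sum test with a patient-level paired comparison, such as a bootstrap over patients of the pooled out-of-fold predictions.
6. Lock the final model, then score Sub-center 1 once.

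The cost is SAP wording, more computing for the inner loops, slightly fewer cases per inner fit and slightly less favourable internal figures. If the sponsor prefers not to nest, the minimum is steps 1 and 6, with no tuning-set result presented as validation.
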